3.2.2.2 Immunogenicity of Pfs230D1M-EPA/Alhydrogel[®] in Healthy Malian Adults

Evaluation of immunogenicity and functional activity for the low dose, unblinded cohorts (Cohort 1, 2) have been completed (**Figure 14**). Pre-existing immunity to Pfs230 was seen prior to vaccination. The majority of subjects in all Arms (B1: 15µg of Pfs230D1M; C1: 16µg of

Pfs25M + 15µg of Pfs230D1M) responded to the vaccine following Vaccination #2. Antibody responses to Pfs230 appeared to persist longer than has been previously seen with Pfs25.

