3.5.1.2 Immunogenicity and Functional Activity

In the unblinded Safety Pilot Phase, immunogenicity results (ELISA) have been completed through study day 224 (**Figure 18**; 8 weeks post Vaccination #3) and functional activity (standard membrane feeding assays; SMFA) have been completed through study day 112 (**Figure 19**; 12 weeks post Vaccination #2).

Figure 18. Antibody responses to Pfs25 and Pfs230 at low and high dosage and with single and co-administration dosing obtained 8 weeks post vaccination #3.

[figure not shown]

Figure 18. Antibody responses to Pfs25 and Pfs230 at low and high dosage and with single and co-administration dosing. Samples obtained 14 days and then at least monthly following receipt of vaccination. Vaccinations received at 0, 1, 6 months. Each individual data point represents the ELISA geometric mean value with black bars represent 95% confidence intervals. Comparison group (dashed lines) is the same dosage used with the Alhydrogel[®] adjuvant from NIAID protocol 15-I-0044.

As expected, no pre-existing immunity was seen prior to vaccination in Malian adults to Pfs25. Most subjects in all Arms receiving Pfs25M (Arm 1a: low dose of Pfs25M, 16µg and Arm 1b: high dose of Pfs25M, 47µg and Arm 3a: low dose of Pfs25M, 16µg and low dose of Pfs230D1M, 13µg and Arm 3b: high dose of Pfs25M, 47µg and high dose of Pfs230D1M, 40µg) responded to the vaccine following Vaccination #1, which is significantly different from the lack of antibody responses seen with the same dosage of Pfs25M but with the Alhydrogel[®] adjuvant. Antibody responses continued to increase with the second vaccination, but were the same or slightly less after the third vaccination. There was no difference in the antibody responses to Pfs25 between Arm 1a versus Arm 1b, nor between those who received the combination of Arm 3a versus Arm 1a and Arm 3b versus Arm 1b, but the overall trend was lower antibody responses to Pfs25 were seen in those individuals that received the combination dose (Arms 3a, 3b) than those who received Pfs25M alone (Arms 1a, 1b).

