Consistent with previous findings, a small percentage of subjects who received Pfs230D1M vaccinations had pre-existing antibodies to the Pfs230D1M vaccine antigen. Similar to Pfs25, most subjects in all Arms receiving Pfs230D1M (Arm 2a: low dose of Pfs230D1M, 13µg and Arm 2b: high dose of Pfs230D1M, 40µg and Arm 3a: low dose of Pfs25M, 16µg and low dose of Pfs230D1M, 13µg and Arm 3b: high dose of Pfs25M, 47µg and high dose of Pfs230D1M,

40µg) responded after one vaccination. Antibody responses were similar between those who received the low dose (Arm 2a) and the high dose (Arm 2b) of Pfs230D1M alone. And as seen with Pfs25M, overall lower antibody responses to Pfs230 were seen in those individuals that received the combination dose (Arms 3a, 3b) than those who received Pfs230D1M alone (Arms 2a, 2b).

Standard membrane feeding assays (SMFA) have been completed in Arms 2a and 2b and associated comparator Arms (Arm 4a, 4b) at two timepoints post Vaccination #2 (2 weeks and 12 weeks) to date. As seen in **Figure 19**, significant functional activity, including transmission blocking activity, can be seen in the Pfs230D1M alone Arms at 2 weeks and persisting even at 12 weeks post Vaccination #2. This is a significant improvement from the lack of activity seen with the same TBV product with the Alhydrogel[®] adjuvant (NIAID protocol #15-I-0044).

Figure 19: Functional activity of Pfs230 vaccinees by SMFA at 2 weeks and 12 weeks post Vaccination #2 in the open label safety cohort.

[figure not shown]

Figure 19. Functional activity of Pfs230 vaccinees by SMFA at 2 weeks and 12 weeks post Vaccination #2 in the open label safety cohort. Samples obtained 14 days and then at least monthly following receipt of vaccination, including at 12 weeks post vaccination #2. Vaccinations received at 0, 1, 6 months. Each individual data point represents an individual mosquito dissection in the SMFAs with the black bars representing the geometric mean oocyst count per mosquito.

Looking at the kinetics of anti-Pfs25 and anti-Pfs230 antibodies, although there is increased durability with the addition of AS01, the rate of decay is unknown. To answer this question, the vaccinated subjects in the pilot arm and some from the main arms will be invited for additional blood draws at 9 and 12 months to evaluate the kinetics of these antibodies.

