14.3 Secondary Objectives

The secondary objective of this study is to determine the antibody response of both vaccines and their combination as measured by ELISA and transmission-blocking assays as measured by SMFA and DSF and the effect on antibody responses of a third dose.

Anti-Pfs25 antibody will be measured by ELISA on vaccination days, 2 weeks after each vaccination, and periodically until study completion. Antibody responses over time will be shown graphically with geometric mean antibodies and the associated confidence intervals based on the t-distribution applied to the log-transformed responses. The smaller (n=5 and n=10) groups are primarily included for safety, and their ELISA response will only be used in an exploratory nature. They will not be included in the main analysis of the secondary endpoint. We will compare antibody and functional assay responses within Arms over time.

We will also look at differences in antibody decline over time in the vaccination groups.

Graphs will display transmission-blocking assays as a function of ELISA antibody levels.

Preliminary results for the SMFA and ELISA have been ascertained for Day 252 (12 weeks post-dose 3). They have been discussed with the scientific advisory board (SAB) and the data safety monitoring board (DSMB). The conclusion to combine groups for the full booster dose was based on the facts that fractional (1/5 the amount of antigen and adjuvant) dosing (marginally) failed ($p=0.0597$) to be statistically significantly different than full dosing when looking at TRA readouts from the SMFA while being statistically significantly different in ELISA titer readouts

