The preliminary data from protocol #15-I-0044 on subjects who had each Pfs25 and Pfs230 ELISA measurements after receiving two and three doses of 47µg Pfs25 + 40µg Pfs230 (using Alhydrogel[®] adjuvant, not AS01 as in this protocol) allow us to estimate the SD of the log transformed Pfs25 ELISA responses at baseline, post vaccination 2 and post vaccination 3. Due to these data still being blinded, we do not report the values for the SD and mean of the log transformed Pfs25 ELISA responses.

Assuming similar values in this trial, there would be over 0.99 power to detect the difference between baseline and post-vaccination 2 and over 0.9 power to detect the difference between post vaccination 2 and post vaccination 3.

In these same preliminary data from protocol #15-I-0044 all control subjects had undetectable levels of Pfs25 ELISA response post 2nd and 3rd vaccination.

Within Arm 2c and using the background information from #15-I-0044, we have greater than 80% power to reject a 2-sided 0.05 level WMW test if the geometric mean Pfs230 ELISA baseline level was 1.6-fold higher geometric mean than the level of detection in the vaccinated group post vaccination 2 (Note: 1.6-fold is lower than what we observed in #15-I-0044, so we treat these numbers as conservative). Given the similarity in SD estimate post vaccination 3, we should have very similar power post vaccination 3 as was calculated for post vaccination 2.

There are three key comparisons regarding ELISA measurements and the booster dose (equivalently dose 4). These include 1) peak titers after dose 4 compared with those following

dose 3; 2) nadir titers at 3 months post dose 4 compared to those post dose 3; and 3) decay rates after dose 4 compared to those after dose 2 and those after dose 3. The power to detect these differences is modest/low due to the expected performance of the booster to perform similarly to the previous doses. However, it is important to note that the primary immunogenicity endpoints will be comparing ELISA titers of each arm 2c and 2d versus the control arm 4c at all time points, which will be powered above 90%.

FUNCTIONAL ASSAYS

SMFA

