Study Day 308 (± 21 days; 140 days after Vaccination #3)

1. Perform basic history and focused physical examination, emphasizing examination of any acute complaints.
2. Record vital signs (blood pressure, temperature, and heart rate).
3. Record AEs and concomitant medications, if applicable.

Study Day 336 (± 21 days; 168 days after Vaccination #3)

1. Perform basic history and focused physical examination, emphasizing examination of any acute complaints.
2. Record vital signs (blood pressure, temperature, and heart rate).
3. Record AEs and concomitant medications, if applicable.
4. Obtain approximately 6 mL of blood for malaria blood smear, malaria PCR, SMFA, and anti-Pfs25M and anti-Pfs230 antibody ELISA.

Re-enrollment visits:

Study Day 420 (-14/+90 days; 252 days after Vaccination #3); Re-screening

1. Explain the study and informed consent document to the subject.
2. Ensure the subject has acknowledged consent by signing or fingerprinting the informed consent document. Ensure that the subject receives a signed copy of the informed consent.
3. Perform basic history and focused physical examination, emphasizing examination of any acute complaints.
4. Record vital signs (blood pressure, temperature, and heart rate).
5. Record AEs and concomitant medications, if applicable.
6. Obtain approximately 6 mL of blood for blood for malaria blood smear, malaria PCR, SMFA, and anti-Pfs230 antibody ELISA,

Study Day 532 (+42 days; 364 days after Vaccination #3)

1. Perform basic history and focused physical examination, emphasizing examination of any acute complaints.
2. Record vital signs (blood pressure, temperature, and heart rate).
3. Record AEs and concomitant medications, if applicable.
4. Obtain approximately 6 mL of blood for blood for malaria blood smear, malaria PCR, SMFA, and anti-Pfs230 antibody ELISA
5. Offer ENGERIX-B (or other approved Hepatitis B vaccine) to those subjects that received TBV(s) during the study.

Bamako/Sotuba Cohort – Arms 1b, 2b, 3b, 4a, 4b (3 Vaccinations; safety cohort)

Study Day 0 (day of Vaccination #1)

The following evaluations/procedures will be completed before vaccination:

1. Verify that informed consent was obtained.
2. Ensure that all inclusion/exclusion criteria are met.
3. Ensure that CBC, ALT, creatinine, HIV/HCV/HBV, and urine results from screening are within protocol-defined limits (see Exclusion Criteria above) before vaccinating.

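### The >0.99 and >0.9 within-arm ELISA powers are for anti-Pfs25, which no 60-subject arm is vaccinated to raise, and Appendix C omits anti-Pfs25 ELISA at the pilot's long-term visits

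*Combined protocol and SAP*

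**What the plan says.** Section 14.3 describes one ELISA measure: "Anti-Pfs25 antibody will be measured by ELISA on vaccination days, 2 weeks after each vaccination, and periodically until study completion". The same paragraph says of the groups of 5 and 10: "They will not be included in the main analysis of the secondary endpoint".

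Section 14.5 (ELISA analysis) plans Wilcoxon signed rank tests of change within the 60 people on one regimen, and Wilcoxon-Mann-Whitney tests against comparator. For the within-arm tests it relies on data from #15-I-0044 that "allow us to estimate the SD of the log transformed Pfs25 ELISA responses at baseline, post vaccination 2 and post vaccination 3". Those data come from people given 47 µg Pfs25 with 40 µg Pfs230 on Alhydrogel. Assuming similar values here, it states "over 0.99 power to detect the difference between baseline and post-vaccination 2 and over 0.9 power to detect the difference between post vaccination 2" (the second comparison is with the response to the third dose). The means and SDs are not given.

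The section also gives two power statements that concern Pfs230 or the main arms: above 80% for a Pfs230 Wilcoxon-Mann-Whitney test in Arm 2c at a 1.6-fold geometric mean, and above 90% for Arms 2c and 2d against Arm 4c.

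For the pilot's added visits at Days 420 and 532, Appendix C says: "Obtain approximately 6 mL of blood for blood for malaria blood smear, malaria PCR, SMFA, and anti-Pfs230 antibody ELISA". Section 3.5.1.2 explains why the visits were added, beginning "Looking at the kinetics of anti-Pfs25 and anti-Pfs230 antibodies". The ELISA row in Appendix B for the pilot covers both antigens.

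**The concern.** The antigen in the ELISA text does not match the vaccine in the arms to be analysed. Section 1.2 suggests how this arose: the main phase was planned as a combination and then changed to Pfs230 alone.

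Two things are at stake. First, the plan's stated power for its within-arm antibody tests, including the effect of a third dose that 14.3 lists as a secondary question, describes a comparison that no 60-subject arm can make. Second, a laboratory working from Appendix C would not run anti-Pfs25 at 9 and 12 months in the people who received Pfs25, although measuring the decay of both antibodies is why those visits exist.

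**Working it through.** **1. Who receives Pfs25 (section 5.1).** Arms 1a (5), 1b (10), 3a (5) and 3b (10): 5 + 10 + 5 + 10 = 30, all in groups of 5 or 10. Main phase: 2c (60) and 2d (60) receive Pfs230D1M; 4c (120) receives ENGERIX-B, then Menactra. Pfs25 recipients among 60 + 60 + 120 = 240: none.

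**2. Reproducing the stated powers.** This cannot be done, because 14.5 withholds the mean and SD on the ground that the data are still blinded. Sections 3.1.4.1 and 3.1.4.2 say #15-I-0044 was unblinded in 2017.

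**3. What the powers imply.** For a paired test at two-sided 0.05, take effective size m = n × 3/π (Wilcoxon efficiency under normality) and power = P(T > t₀.₉₇₅) for noncentral t with m − 1 df and noncentrality d√m, where d is mean difference over SD of differences. With n = 60, m = 57.3.
- Power 0.99 needs d ≈ 0.58; simulated signed rank power 0.989.
- Power 0.90 needs d ≈ 0.44; simulated 0.897.
- At the same d values, a Pfs25 pilot arm of 10 has power of about 0.35 and 0.22.

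**4. Are they plausible for Pfs25 with 60 people?** As an illustration only, use the Pfs25H/Alhydrogel results in section 3.1.2.2 (a different construct). Geometric means are 93.05 (95% CI 70–122, n = 45) after dose 2 and 169.6 (127–225, n = 44) after dose 3.
- SD of ln titer = [ln(upper/lower)/2] ÷ t₀.₉₇₅ × √n, giving 0.92 and 0.94.
- Difference = ln(169.6/93.05) = 0.60.
- Within-subject correlation is not given. Assuming 0 to 0.7, d runs from 0.46 to 0.83.
- Power is 0.92 to above 0.99 at n = 60, and 0.24 to 0.62 at n = 10.

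So the >0.9 figure is credible for Pfs25 in an arm of 60, but this trial has no such arm.

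**5. Can they be carried over to Arms 2c and 2d?** Antigen and adjuvant both differ. In Arm 2d the third dose is also fractional (8 µg), so a dose 2 to dose 3 change after full dosing is not its comparison. Even for Pfs25, this trial's pilot reports: "Antibody responses continued to increase with the second vaccination, but were the same or slightly less after the third vaccination". That sits badly with assuming a rise like the one seen with Alhydrogel.

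**6. The Pfs230 statement for Arm 2c.** Treat it as a shift with equal SDs (a simplification, since 14.5 refers to the detection limit). The largest SD of ln titer giving 80% power is ln(1.6) ÷ [(1.96 + 0.84) × √(1/m₁ + 1/m₂)], with ln(1.6) = 0.470.
- 60 against 60: about 0.90.
- 60 against 120: about 1.04.

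No Pfs230 SD is given, so this cannot be confirmed either. The benchmark is the detection limit, while section 3.2.2.2 says: "Pre-existing immunity to Pfs230 was seen prior to vaccination".

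**7. Long-term pilot visits.**
- Section 3.5.1.2: kinetics of both antibodies.
- Appendix C, Day 336: both ELISAs.
- Appendix C, Days 420 and 532, all pilot arms: anti-Pfs230 only.
- Appendix B: one ELISA row for both antigens. The 6 mL at the added visits fits 0.5 (smear) + 0.5 (PCR) + 5 (serum). The printed table is damaged, and its fourth-vaccination page uses the same combined label for Arms 2c, 2d and 4c, so the label alone is not decisive.

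Under Appendix C, Arms 1a and 1b (5 + 10 = 15) have no vaccine-antigen ELISA at these visits, and Arms 3a and 3b (5 + 10 = 15) have one of two.

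**The case against.** The rest of the plan does not overlook Pfs230. Anti-Pfs230 IgG is a separate secondary endpoint for all arms (5.2.2), and 14.3 opens by referring to each vaccine and their combination. The tests in 14.5 name no antigen, and Appendix C schedules anti-Pfs230 throughout for Arms 2c, 2d and 4c. The Day 252 comparison already reported for those arms was anti-Pfs230, with p<0.0001 for each vaccine arm against control (3.5.2.2). A reader might infer that the main secondary analysis as a whole tests an antibody nobody analysed was vaccinated to raise. The documents do not support that; the defect lies in one measurement sentence and one pair of power figures.

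A reader might also infer that true power for dose 2 to dose 3 is about 0.05, because the pilot saw no rise. That holds only if the true change is exactly zero. The pilot remark is verbal, concerns Pfs25 arms of 5 and 10 with titers in a figure not shown, and describes no planned 60-subject test.

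On baseline immunity, section 3.5.1.2 reports pre-existing anti-Pfs230 in only a small percentage of pilot vaccinees, and the Wilcoxon-Mann-Whitney test was chosen partly to handle values at the detection limit. Nothing shows that the Pfs230 power borrowed the statement about undetectable Pfs25 in controls.

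Finally, section 14.1 calls the study exploratory, 14.5 discloses the adjuvant difference, and recalculated power cannot change enrolment. All of this stands and limits the consequence. It does not make the quoted powers apply to any analysed arm, and it does not settle which ELISA is run at Days 420 and 532.

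**Conclusion.** The point holds in limited form. The >0.99 and >0.9 figures are attached to the wrong antigen for every 60-subject arm and cannot be checked from the documents. They are not shown to be arithmetically wrong, and with 60 Pfs25 recipients the second would be plausible under the illustration above. Section 14.3 names only anti-Pfs25 while excluding all 30 Pfs25 recipients from the main analysis; 0 of 240 main-phase subjects receive it. The section's Pfs230 and between-arm powers exist but also come without inputs. No power for anti-Pfs230 is offered here, because the documents give no mean or SD for it.

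The Day 420 and 532 matter is an internal contradiction, not an established omission. It might be read as 30 people losing their long-term readout. On the documents it is at most 15 with no vaccine-antigen ELISA and 15 with one of two, and only if Appendix C is followed over Appendix B and section 3.5.1.2.

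The back-calculation assumes n = 60, two-sided 0.05 and approximately normal differences on the log scale.

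**What to change.** - **Section 14.3:** name anti-Pfs230 as the ELISA outcome for Arms 2c, 2d and 4c, with anti-Pfs25 exploratory in the pilot.
- **Section 14.5:** withdraw the Pfs25-based powers, or restate them for anti-Pfs230 with mean, SD and n shown, separately for full (2c) and fractional (2d) third doses. Set the comparator benchmark from the control anti-Pfs230 distribution rather than the detection limit alone. Reword the Arm 2c sentence, which mixes a baseline level with a post-vaccination one.
- **Appendix C, Days 420 and 532:** reconcile with Appendix B and section 3.5.1.2 by adding anti-Pfs25 ELISA for Arms 1a, 1b, 3a and 3b.

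The cost is text, one recalculation, and one further ELISA on serum already drawn: at most 30 people × 2 visits = 60 samples. No visit, blood volume or sample size changes.

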14.5 Sample Size and Power Calculations

SAFETY

The arms of five subjects are sized for safety, as the higher dose is expected to be necessary for an adequate immune response. In these arms (Arms 1a, 2a, 3a), 5 subjects each will receive 16 μg of Pfs25M-EPA/AS01 or 13 μg Pfs230D1M-EPA/AS01 or the combination of both.

Vaccination arms of 5 subjects gives a probability of at least 0.80 for detecting 1 or more serious or severe AEs that occur with a probability of 0.275 or more per subject.

For each dose level that has a ($n=10$) in Arms 1b, 2b, 3b, vaccination of 10 subjects gives a probability of at least 0.90 for detecting 1 or more serious or severe AEs that occur with a probability of 0.206 or more per subject.

For each dose level that has a (n=60) in Arms 2c, 2d, and 4c, vaccination of 60 subjects gives a probability of at least 0.90 for detecting 1 or more serious or severe AEs that occur with a probability of 0.038 or more per subject.

If we combine all treated groups in Mali (Arms 1a, 1b, 2a, 2b, 3a, 3b, 2c and 2d), 165 subjects, we have 95% power to detect 1 or more serious or severe AEs that occur with a probability of 0.018 or more per subject. Due to arms having varying doses, combinations and administration villages, this analysis would only be done to catch an AE that transcended these discrepancies.

We will compare all AE event proportions between the control arm and treated arm by Fisher's exact test.

ELISA ANALYSIS

There are several questions of interest based on the antibody response information after the 2nd, 3rd and for arms 2c, 2d, and 4c, a 4th (booster) doses of the respective vaccines. We are interested in the change in ELISA values from baseline to after a given number of doses of vaccine, and the change in ELISA values between doses. For this we will use Wilcoxon signed rank tests (WSRT) within the 60 subjects receiving a given vaccine regimen. We are also interested in the effect of a given number of vaccinations on the ELISA responses as compared to comparator. This comparison can be made by Wilcoxon Mann Whitney (WMW) test, which accommodates the limit of detection issues that may exist for ELISA results.

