Using blinded SMFA data from #15-I-0044, a WMWT comparing 60 TRAs of the vaccine arm to 60 TRAs of the control, we anticipate at least 80% power to detect a difference in TRAs of 18% (simulation-based power calculations). If TBAs are used, we will standardize the TBAs to a common target control mean first. The standardization will utilize the estimand that comes from a zero-inflated negative binomial with random effects for feed and container of mosquito. TRAs can be combined across feeds or calculated within feeds as they do not require the same standardization as that of TBAs.

DSF

Using the data from the primary DSF evaluation period of study #13-I-N109 and #15-I-0044 we were able to do power calculations for this study. The power calculations are quite sensitive to the infectivity rate, which varies from year to year. Taking a weighted average of 2014 and 2015 data we estimate infectivity was 14.8% (the percentage of subjects in the control arm that had at least one positive DSF). Using this same % and comparing 108 subjects (this number assumes 10% dropout) of the combined Arms 2c and 2d we will have ~85% power to detect 80% vaccine effect through the (0,1) infective/non-infective way of quantifying each DSF with 32 DSF per person and 30 mosquitoes per cup. The (0,1) infective/non-infective way of quantifying each DSF involves declaring a cup as infective if any of the 30 mosquitoes is infected and conversely non-infective if and only if all 30 mosquitoes are not infected. While combining arms that have full dosing in one and fractional dosing in the other assumes they are having similar effects, this assumption is deemed acceptable in order to power the analysis. If infectivity drops to 10.3%, then the power to detect 80% vaccine effect under same conditions is about 40%. It is important to note that in 2016 only 15 mosquitoes were used per cup and only 12 DSFs per person were conducted. Thus, we are treating the 10.3% infectivity as a “worse case scenario” for the 30 cup / 24 DSFs set-up as proposed in this protocol. A binomial family GEE model will be used to account for repeated measurements.

On average each feed week we had about 3% positivity over all subjects. The (0,1) infective/non-infective way of quantifying DSF is likely an over-simplification of the true system. As well, this way of quantifying the DSF will have lower power when the vaccine is leaky rather than all or nothing.

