For the booster (dose 4), the combined Arms 2c and 2d will be evaluated vs. controls as the primary endpoint.

DSF in conjunction with SMFA

As there will be simultaneous blood draws, a unique opportunity to investigate SMFA predicting zero inflated DSF measurements will be pursued. Simple linear regression models will be explored.

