14.6 Randomization

See [Section 8.2](#) for more information.

Enrollment into the Bamako/Sotuba, Mali portion of the study will be randomized as follows:

- Arms 1a and 2a will be enrolled 1-1 with random block based on time of enrollment/randomization;
- Arm 3a will not have a concurrent arm, so there will be no randomization for that arm;
- Arms 1b, 2b and 4a will be enrolled 1-1-1 with the same style of random block based on time of enrollment/ randomization;
- Arms 3b and 4b will be enrolled 1-1 with random block based on time of enrollment/randomization.

Enrollment into the Bancoumana/Doneguebougou, Mali portion of the study will be randomized in random blocks of size no greater than 8 and stratified by village. In order to accomplish this, a list of all enrolled subjects will be given to the study statistician for the first randomization. As subjects that dropout after randomization, and are not vaccinated, cannot be replaced, randomization and first vaccination should occur as close in time as possible to avoid having subjects in the ITT efficacy and safety analyses that have never received vaccination or comparator. Randomization lists are not produced pre-enrollment to reduce the risk of on-site operational error in randomization assignment, which given the stratified nature of the randomization would require management of several lists.

Randomization will occur **between arms** as follows in the Bancoumana/Doneguebougou study:

- Arms 2c, 2d, and 4c will be enrolled 1-1-2 with random block sizes no greater than 8.

Randomization between the arms allows for causal comparisons of ELISA and functional assay responses.

15 Human Subject Protections and Ethical Obligations

This research will be conducted in compliance with the protocol, Good Clinical Practices (GCP), and all applicable regulatory requirements.

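### Section 14.5 (DSF): power of 85% at 14.8% infectivity and 40% at 10.3% cannot share the same conditions; 40% understates the pooled comparison by roughly 15 to 35 points

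*Combined protocol and SAP*

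**What the plan says.** The DSF part of section 14.5 defines infectivity as the share of control subjects with at least one positive feed. The base value is given as follows: "Taking a weighted average of 2014 and 2015 data we estimate infectivity was 14.8" per cent. The base power is stated by "comparing 108 subjects (this number assumes 10% dropout) of the combined Arms 2c and 2d we will have ~85% power" for an 80% vaccine effect, with 32 feeds per person and 30 mosquitoes per cup. The low-transmission case follows: "If infectivity drops to 10.3%, then the power to detect 80% vaccine effect under same conditions is about 40" per cent. The paragraph calls 10.3% a worst case, but there it describes the set-up as 24 feeds.

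Pooling the full and fractional third-dose arms is defended on power grounds: "this assumption is deemed acceptable in order to power the analysis". For the booster, "the combined Arms 2c and 2d will be evaluated vs. controls as the primary endpoint". The planned analysis is a binomial GEE. The plan does not say which test, alpha or control number produced either DSF power figure.

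**The concern.** As worded, only control infectivity changes between the two figures, from 14.8% to 10.3%, a relative fall of about 30%. A fall of that size should not take power from 85% to 40% in a fixed comparison.

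The 40% is the plan's only low-season power for the booster's main DSF comparison. A reader will use it to judge how informative a null result would be in a weak season, and a null result at 40% power reads differently from one at 65%. Power is also the stated reason for pooling two regimens, so a wrong worst-case figure misstates what a weak season costs and may hide what pooling gains.

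**Working it through.** **Inputs**
- Control infectivity: 14.8% (base) and 10.3% (worst case), section 14.5. The 10.3% matches the comparator group after vaccination #4 in Table 7: 4/39 = 10.26%.
- Effect 80%, so the vaccine-group rates are 0.2 × 14.8% = 2.96% and 0.2 × 10.3% = 2.06%.
- Vaccinees: 120 × 0.9 = 108, as stated.
- Controls: not stated for the DSF power. Section 14.6 says "Arms 2c, 2d, and 4c will be enrolled 1-1-2 with random block sizes no greater than 8" and section 5.1 gives Arm 4c as 120, so 120 × 0.9 = 108 (derived).
- One vaccine arm: 60 × 0.9 = 54 (derived).
- Alpha: two-sided 0.05 (assumed; section 14.5 uses it for an ELISA power statement).

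**Reproducing the 85%.** Exact power of Fisher's test is the sum, over all event counts a and b, of Bin(a; 108, p_control) × Bin(b; 108, p_vaccine), counting only tables with two-sided p ≤ 0.05. At 14.8% v 2.96% this is 85.1%, which matches the plan.

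**Changing only the infectivity.** The same sum at 10.3% v 2.06% is 65.5%.

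**Other methods, 108 v 108**

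| Method | 14.8% | 10.3% |
|---|---|---|
| Fisher's exact | 85.1% | 65.5% |
| Chi-square, continuity-corrected | 83.8% | 63.0% |
| z test, pooled variance | 86.9% | 71.3% |
| z test, unpooled variance | 87.8% | 72.3% |
| Chi-square, uncorrected | 90.5% | 74.8% |
| Arcsine | 90.4% | 76.6% |

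Pooled z at 10.3%: the mean rate is 0.0618; null SE = √(0.0618 × 0.9382 × 2/108) = 0.03277; alternative SE = √((0.103 × 0.897 + 0.0206 × 0.9794)/108) = 0.03228; (0.0824 − 1.96 × 0.03277)/0.03228 = 0.563; Φ(0.563) = 71.3%.

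**Check that does not depend on the test.** If some test has 85% power at 14.8% and its information scales with the event rate, then (1.960 + 1.036) × √(10.3/14.8) = 2.50, and Φ(2.50 − 1.96) = 70.5%. For 40% power the information must fall to ((1.960 − 0.253)/2.996)² = 0.324 of its base value, a control rate of 0.324 × 14.8% = 4.8%. By exact Fisher at 108 v 108, 40% is reached at about 7%.

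**Planned model.** Robust-variance GEE simulations under assumed feed-level clustering that gave roughly 83% to 88% at 14.8% gave roughly 54% to 73% at 10.3%. With infectivity held at the stated value, using 24 rather than 32 feeds made little difference: in one matched scenario, 84–87% fell to 63–71% with 24 feeds, and 86–88% fell to 61–69% with 32. Each range reflects how a vaccine arm with no positive feed is counted.

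**Where 40% does appear.** Fisher's test with 54 vaccinees v 108 controls gives 64.3% at 14.8% and 39.5% at 10.3%; with 54 v 120 at 10.3% it gives 40.6%.

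**The case against.** The strongest objection is that the method is assumed. The DSF paragraph names no test, describes feeds as individually infective or not, and plans a GEE; Fisher's test appears in section 14.5 only for adverse-event proportions. This stands. The 65% is specific to Fisher's test and must carry its range. It does not rescue the pair of figures, because a claim of unchanged conditions requires one method for both, and no method tried gave 85% and 40% together. Some GEE scenarios fell to about 43% to 48% at 10.3%, but they started at only about 57% to 70%.

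A second objection is that the season behind the 10.3% differed in more than subject-level infectivity. In Table 7, positive comparator feeds fell from 18/497 (3.6%) to 4/452 (0.9%), and section 14.5 notes fewer mosquitoes and feeds in 2016. A calculation driven by feed-level data could have changed several inputs. That is possible, but then the conditions were not the same and the sentence is still wrong as written.

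A reader might also infer that the 40% is the single-arm figure carried into the wrong sentence. The match is close, but the documents nowhere say so, and it rests on an assumed test and a derived control number.

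Finally, the error is conservative, DSF is a secondary endpoint in a study that section 14.1 calls exploratory, and section 14.5 already warns that power is sensitive to infectivity. All of this is fair and limits the consequences.

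**Conclusion.** The two DSF power figures are inconsistent as written. For combined Arms 2c and 2d against Arm 4c at about 108 v 108, a method that gives roughly 85% at 14.8% gives about 55% to 77% at 10.3%, and 65.5% under the Fisher's test that reproduces the 85%. Against the stated 40%, the understatement is 15 points at the low end (55 − 40), about 25 for Fisher (65.5 − 40), and a little over 35 at the top (77 − 40).

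This rests on two-sided alpha 0.05, a control number derived from the allocation with 10% dropout, and assumed clustering in the GEE runs. The documents do not support two stronger readings: that 65% is the correct figure whatever the method, or that the 40% is known to come from one unpooled arm. Nor does the finding argue against pooling or the booster comparison; the pooled comparison has more worst-case power than the plan says.

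**What to change.** Recompute the 10.3% figure with the same method, group sizes and number of feeds used for the 85%, and replace the 40% with the result (about 65% if Fisher's test was used). Settle whether 32 or 24 feeds apply, since the paragraph cites both. If the 40% was calculated for a single arm or for other feed conditions, keep it under that label and remove the claim that conditions are unchanged. Beside each DSF power figure, state the test, alpha, both group sizes and number of feeds. If the power method differs from the planned GEE, say so.

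The cost is one or two sentences in section 14.5 and a rerun of the sponsor's own calculation. The design, sample size and analysis do not change.
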